### **3.4 Exclusion Criteria**

**3.4.1** Known allergy to any drug used in the study;

**3.4.2** Pregnant or breastfeeding women;

**3.4.3** Participated in other clinical trial involving another drug within 4 weeks prior to the initiation of the study;

**3.4.4** Prior treatment with bevacizumab or small molecule tyrosine kinase inhibitors of VEGFR (e.g., famitinib, sorafenib, sunitinib, regorafenib, apatinib and fruquintinib);

**3.4.5** Recurrence of nasopharyngeal lesions after radiotherapy, followed by secondary radiotherapy;

**3.4.6** Palliative radiotherapy for symptom control within 28 days prior to enrollment;

**3.4.7** Systemic immunomodulatory therapies (including but not limited to interferon and interleukin-2) within 28 days prior to enrollment;

**3.4.8** Tumor cell invasion in vital blood vessels (e.g., encasement of internal carotid artery/vein) by MRI; or the patient's tumor is very likely to affect vital blood vessels and cause fatal hemorrhage during treatment, as judged by investigators;

**3.4.9** History of severe hemorrhage, and any other Grade  $\geq 3$  bleeding or hemorrhage per CTCAE 4.0 within 4 weeks prior to screening;

**3.4.10** Coagulation abnormalities, and evidence or history of bleeding diathesis (INR

within normal range without the use of anticoagulants 14 days prior to signing the informed consent form); treatment with anticoagulants or vitamin K antagonists, such as warfarin, heparin or analogues thereof; on the premise of the prothrombin time as International Normalized Ratio (INR)  $\leq 1.5$ , low-dose warfarin (1 mg orally, once a day) or low-dose aspirin (no more than 100 mg daily) is allowed for preventive purposes;

**3.4.11** Unstable angina and/or congestive heart failure or vascular disease requiring hospitalization (e.g., aortic aneurysm or peripheral venous thrombosis requiring surgical repair), or other cardiac impairment that, as judged by investigators, may affect the safety evaluation of the study drug (e.g., poorly controlled arrhythmia, myocardial infarction or ischemia) within 12 months prior to enrollment;

**3.4.12** Hypertension that is not well controlled with a single antihypertensive drug (defined as systolic blood pressure  $> 140$  mmHg, and diastolic blood pressure  $> 90$  mmHg); or combination therapy with two or more antihypertensive drugs; clinically significant (e.g., active) cardiovascular diseases - such as cerebrovascular accident ( $\leq 6$  months prior to randomization), myocardial infarction ( $\leq 6$  months prior to randomization), unstable angina, Class II congestive heart failure or above per New York Heart Association (NYHA), or severe arrhythmias that cannot be controlled with drugs or have potential impact on study treatment;

**3.4.13** Esophageal and fundal gastric varices, active ulcers, intestinal perforation, or intestinal obstruction within 6 months prior to enrollment;

**3.4.14** History of abdominal fistula, gastrointestinal perforation, intra-abdominal abscess, or acute gastrointestinal bleeding within 6 months prior to enrollment;

**3.4.15** Multiple factors affecting oral administration and absorption of the study drug (e.g., inability to swallow, postoperative period following gastroenterectomy, chronic diarrhea and intestinal obstruction);

**3.4.16** Occurrence of arterial/venous thrombosis events, Grade  $\geq 3$  venous thromboembolism per NCI CTCAE, such as cerebrovascular accident (including transient ischemic attacks), deep vein thrombosis (except for venous thrombosis triggered by intravenous catheterization during prior chemotherapy that has been

cured as judged by investigators) and pulmonary embolism within 6 months prior to enrollment;

**3.4.17** Objective evidence of pulmonary fibrosis, interstitial pneumonia, pneumoconiosis, radiation pneumonitis, drug-related pneumonia and severely impaired lung function, etc. in the past and at present;

**3.4.18** Exacerbation of chronic obstructive pulmonary disease (COPD) or other respiratory diseases requiring hospitalization within 28 days prior to enrollment;

**3.4.19** Active pulmonary infection and/or acute bacterial or fungal infection requiring intravenous antibiotic treatment within 28 days;

**3.4.20** Obvious jaundice due to abnormal liver function within 7 days;

**3.4.21** Renal insufficiency: Urinalysis shows proteinuria > 2+ and 24-hour urine protein test demonstrates urine protein > 1.0 g;

**3.4.22** Minor surgery (including catheterization, excluding peripherally inserted central catheterization) within 2 days prior to enrollment;

**3.4.23** Major surgery within 28 days prior to enrollment;

**3.4.24** Treatment with a strong CYP3A4 inhibitor within 1 week prior to enrollment or treatment with a strong CYP3A4 inducer within 2 weeks prior to enrollment;

**3.4.25** Chronic non-healing wounds or incompletely healed fractures;

**3.4.26** Symptomatic metastases to the central nervous system (e.g., cerebral edema requiring hormonal intervention, or progression of brain metastasis) (proven or suspected);

**3.4.27** Severe or uncontrolled infection;

**3.4.28** History of psychotropic drug abuse and unable to quit, or history of mental disorders;

**3.4.29** History of immunodeficiency, including positive HIV result, or other acquired and congenital immunodeficiency diseases, or history of organ transplantation;

**3.4.30** Virological tests during the screening period show either of the following: Positive HBsAg result and HBV DNA titer in the peripheral blood  $\geq 1 \times 10^3$  copies/L; positive anti-HCV result;

**3.4.31** History of other malignant tumors in the past 5 years, except cured skin basal

cell carcinoma, cervical carcinoma in situ and superficial bladder cancer;

**3.4.32** Concomitant diseases that may severely impair the safety of patients or make the patients unable to complete the study, as judged by investigators.

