### **3.3 Inclusion Criteria**

**3.3.1** Histopathological diagnosis of differentiated or undifferentiated locally recurrent or metastatic NPC (WHO Stage II-III);

**3.3.2** Patients with clinical stage IVB NPC [Appendix I, AJCC staging system for nasopharyngeal cancer, 8th edition] after failure of first-line platinum-based chemotherapy (monotherapy or combination therapy) and second-line single-agent or combination chemotherapy or targeted therapy. Treatment failure is defined as progression during or after chemotherapy after recurrence/metastasis; progression within 6 months after concurrent chemoradiotherapy is considered first-line treatment. All regimen changes due to drug intolerance are not considered treatment failure;

**3.3.3** No history of other malignant tumors, and having no other malignant tumors at the time of diagnosis;

**3.3.4** Male or female patients aged 18–70 years;

**3.3.5** ECOG performance status score of 0–2;

**3.3.6** Estimated survival  $\geq 3$  months;

**3.3.7** Non-lactating women and those of childbearing age must have a negative pregnancy test (serum or urine) within 14 days prior to enrollment, and be willing to take effective contraceptive measures during the study;

**3.3.8** At least one measurable lesion per RECIST ( $\geq 10$  mm in longest diameter by B-scan, MRI or spiral CT scan, and having not undergone radiotherapy);

**3.3.9** Laboratory tests must meet the following criteria:

- Blood routine: Neutrophil count (ANC)  $\geq 1.5 \times 10^9/L$ , platelet count (PLT)  $\geq 100 \times 10^9/L$ , and hemoglobin (HGB)  $\geq 90$  g/L;
- Liver function: Total bilirubin  $\leq 1.5$  times the upper limit of normal (ULN); blood aspartate aminotransferase (AST) and blood alanine aminotransferase (ALT)  $\leq 2.5 \times$  ULN (or  $\leq 5 \times$  ULN for subjects with liver metastases); and alkaline phosphatase  $\leq 5 \times$  ULN;

- Renal function: Serum creatinine (Cr)  $\leq 1.5 \times$  ULN; and creatinine clearance  $\geq 50$  mL/min;
- Urinalysis: Urine protein  $< 2+$  (subjects with baseline urine protein of  $\geq 2+$  should undergo a 24-hour urine protein test within 7 days and can be enrolled only when urine protein  $< 1$  g);
- Coagulation function: INR and APTT  $\leq 1.5 \times$  ULN;

**3.3.10** No severe cardiopulmonary dysfunction;

**3.3.11** Sign the informed consent form;

**3.3.12** Ability to comply with the study protocol.

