#### **4.6.3 Increased blood pressure**

Increased blood pressure is the most common adverse reaction of VEGFR inhibitors. Previous clinical studies have shown that the incidence of hypertension events was high (about 13.61% for grade 3 or higher) in patients receiving Anlotinib Hydrochloride Capsules. Therefore, blood pressure should be measured daily for the first 6 weeks of dosing and 2–3 times a week during the subsequent dosing period.

In case of hypertension, the investigators are recommended to handle the event as follows:

- Grade 1: Prehypertension (SBP 120–139 mmHg or DBP 80–89 mmHg):  
Lack of indications for antihypertensive drugs, only blood pressure

monitoring is required;

- Grade 2: Stage I hypertension (SBP 140–159 mmHg or DBP 90–99 mmHg): Requires medical interventions; Repeated or persistent ( $\geq 24$  h), symptomatic SBP increases by  $> 20$  mmHg or increases to  $> 140/90$  mmHg compared to previous normal range; Requires monotherapy and blood pressure monitoring; Thiazide diuretics are commonly used, and angiotensin-converting enzyme inhibitors (ACEIs), angiotensin II receptor blockers (ARBs),  $\beta$ -blockers, and calcium channel blockers may also be considered;
- Grade 3: Stage II hypertension (SBP  $\geq 160$  mmHg or DBP  $\geq 100$  mmHg): Requires medical intervention; Requires multi-drug therapy, usually thiazide diuretics combined with ACEIs,  $\beta$ -blockers or calcium channel blockers;
- Grade 4: Life-threatening (e.g., malignant hypertension, transient or permanent neurologic deficit, hypertension emergency): Requires urgent intervention;

If grade 3/4 hypertension (SBP  $\geq 180$  mmHg or DBP  $\geq 110$  mmHg) is observed, anlotinib should be interrupted; If grade 3/4 hypertension is observed after anlotinib resumption, treatment should be continued at a lower dose. If grade 3/4 hypertension persists, discontinuation is recommended.

- Hypertension emergencies are defined as having DBP  $> 120$  mmHg accompanied by acute or progressive target organ damage (such as brain infarction, intracranial or subarachnoid hemorrhage, and hypertensive encephalopathy). Progressive or accelerated hypertension on the basis of chronic primary hypertension is the most common (about 40% to 50%) hypertension emergency. Treatment should be discontinued once a hypertension emergency is observed. The subject should withdraw from the clinical study and receive specialized cardiovascular treatment in time.

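### Exclusion 3.4.12 requires both systolic > 140 and diastolic > 90 mmHg, so a patient on one antihypertensive drug with only one pressure raised, however high, passes the numeric rule

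*Protocol*

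**What the plan says.** Section 3.4.12 has three limbs. The first excludes "Hypertension that is not well controlled with a single antihypertensive drug (defined as systolic blood pressure"; the definition then gives a systolic limit of > 140 mmHg and a diastolic limit of > 90 mmHg, and the words that join the two limits are "mmHg, and diastolic blood pressure". The second is "or combination therapy with two or more antihypertensive drugs", which excludes at any pressure. The third begins "clinically significant (e.g., active) cardiovascular diseases - such as cerebrovascular accident" and lists cardiovascular conditions without a blood-pressure limit.

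Two other criteria could bear on the same patients: inclusion 3.3.10 ("No severe cardiopulmonary dysfunction") and exclusion 3.4.32 ("Concomitant diseases that may severely impair the safety of patients or make the patients unable to complete the study, as judged by investigators"). Neither gives a pressure.

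For patients on treatment, section 4.6.3 grades hypertension with 'or'. One entry is "Grade 2: Stage I hypertension (SBP 140–159 mmHg or DBP 90–99 mmHg"); the next, "Grade 3: Stage II hypertension (SBP" ≥ 160 mmHg or DBP ≥ 100 mmHg), has the same form. Its interruption rule is also an 'or' rule: SBP ≥ 180 or DBP ≥ 110 mmHg. The hypertension table in section 4.4 keeps the dose at Grades 1 and 2. At Grade 3 it delays dosing until Grade 2 or lower and then reduces the dose.

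**The concern.** An exclusion for uncontrolled hypertension should act when either pressure is too high. Joined by 'and', the rule acts only when both are, so isolated systolic or isolated diastolic hypertension passes at any height. The rule also ranks patients the wrong way round: it can turn away a moderate combined elevation and let in a severe isolated one.

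This matters because section 4.6.3 calls raised blood pressure the most common adverse reaction of the drug class and gives about 13.61% Grade 3 or higher for anlotinib. A patient could start 12 mg daily at a pressure that, arising on treatment, would delay dosing under section 4.4 or interrupt it under section 4.6.3.

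**Working it through.** The plan states no figure to reproduce. The check is a logical test of the criterion against the protocol's own grades.

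**Inputs**

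- Entry limits, section 3.4.12: SBP > 140, DBP > 90 mmHg, joined by 'and'.
- Grade 2, section 4.6.3: SBP 140–159 or DBP 90–99.
- Grade 3, section 4.6.3: SBP ≥ 160 or DBP ≥ 100.
- Interruption level, section 4.6.3: SBP ≥ 180 or DBP ≥ 110.

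**Rules compared for a patient on one drug**

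- As written: excluded if SBP > 140 and DBP > 90.
- Alternative: excluded if SBP > 140 or DBP > 90.

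The four readings are illustrations chosen for this check.

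| Reading | 4.6.3 grade | Caught by 'and' | Caught by 'or' |
|---|---|---|---|
| 165/85 | 3 (165 ≥ 160) | no (85 ≤ 90) | yes |
| 138/104 | 3 (104 ≥ 100) | no (138 ≤ 140) | yes |
| 185/88 | 3, above the interruption level (185 ≥ 180) | no (88 ≤ 90) | yes |
| 150/95 | 2 | yes | yes |
| Total caught | | 1 of 4 | 4 of 4 |

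**Margin under 'or'.** The highest one-drug reading not caught is 140/90. Its distance to the Grade 3 floor is 160 − 140 = 20 mmHg systolic and 100 − 90 = 10 mmHg diastolic. No one-drug patient with a Grade 3 screening reading then passes.

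**By number of antihypertensive drugs**

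- Two or more: excluded by the second limb at any pressure.
- One: the numeric limit applies, and 'or' repairs it.
- None: the first limb speaks of control on a single drug, so an untreated patient at 170/105 (Grade 3) may fall outside it whichever connector is used. Only a wording that names untreated patients settles this.

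**Existing procedures.** Section 5.1 requires blood pressure within 7 days before dosing, and section 5.3 does not ask for a repeat before the first dose if that was done. A recent reading is therefore available; the fault lies in the rule applied to it. Daily measurement under section 4.6.3 starts with dosing, after the entry decision.

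**The case against.** The strongest reply is that the comma before 'and' lets the definition be read as a list of two separate limits, each of which must be met for control. That may well be the intent. But a literal reader and a reader for intent would then decide differently on the same patient, which is itself a reason to correct the text.

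Second, section 4.6.3 governs handling on treatment and sets no entry standard, and it is not a clean benchmark. It defines Grade 3 from 160 or 100 mmHg, yet gives 180 or 110 mmHg for Grade 3/4 in the interruption rule. It also uses the pair > 140/90 without a connector and defines a hypertension emergency by diastolic pressure alone. Of the three missed readings, only 185/88 reaches the interruption level. This stands: the entry rule is out of line with section 4.6.3, not in strict contradiction with it. The delay at Grade 3 in section 4.4 still points the same way.

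Third, an investigator who sees 185/88 may exclude under 3.4.32, and daily measurement for the first six weeks would detect trouble soon. These safeguards limit the consequence, but one is discretionary and the other comes after the first dose.

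Fourth, 'or' would also exclude a one-drug patient at 142/80, which is Grade 2 and would keep the original dose under section 4.4. That is a real cost. However, the present rule already excludes Grade 2 readings such as 150/95, and the limits of 140 and 90 are the plan's own; the change only makes each of them effective.

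**Conclusion.** The concern holds. As worded, the numeric definition in 3.4.12 does not catch isolated systolic or isolated diastolic hypertension in a patient on one antihypertensive drug. It passes Grade 3 readings, including one above the 180 mmHg interruption level, while it excludes a Grade 2 reading. The conclusion rests on the literal reading of 'and' and is confined to the numeric rule; other criteria may catch some of these patients by judgement, but none sets a pressure limit for them.

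The number of patients affected is not given in the protocol and is not estimated here. The consequence is for eligibility and safety only. The correction should be made, although no efficacy conclusion depends on it.

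**What to change.** Minimum change to 3.4.12: replace 'and' with 'or', giving SBP > 140 mmHg or DBP > 90 mmHg on a single antihypertensive drug.

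Preferred wording, which also reaches untreated patients: blood pressure > 140 mmHg systolic or > 90 mmHg diastolic, whether untreated or on a single antihypertensive drug; or treatment with two or more antihypertensive drugs. The cardiovascular limb stays as it is.

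The cost is an eligibility amendment of one word or one clause, with ethics committee approval and regulatory filing under section 12. No procedure is added, because section 5.1 already requires the measurement. There may be some more screen failures, for example at 142/80 on one drug. Section 10 plans enrolment to end in March 2021; if it has closed, the change screens no one in this trial, but the wording should not be carried into a later protocol.

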### **3.5 Withdrawal Criteria**

**3.5.1** Subjects voluntarily withdraw the informed consent and request to withdraw from the clinical trial;

**3.5.2** Disease progression with medical radiological evidence (e.g., CT, MRI, B-scan examination, etc.) or clinical progression clearly judged by investigators (the reasons for judging progression should be recorded in detail);

**3.5.3** Pregnancy in female subject occurs during the study;

**3.5.4** Other conditions that necessitate the withdrawal from the study, as considered by investigators (the withdrawal reasons should be recorded in detail);

**3.5.5** The sponsor terminates the study due to safety concern or other special reasons.

## **4. STUDY DRUG**

### **4.1 Strength and Shelf Life of Study Drug**

Name of Drug	Characters	Strength	Directions for Use	Shelf Life
Anlotinib	The contents are	12 mg, 10	Oral	18
Hydrochloride	white or off-white	mg, 8 mg		months
Capsules	powder or granules			

### **4.2 Storage of Study Drug**

Store sealed under 25°C and away from light

### 4.3 Route of Administration

Based on the human pharmacokinetic studies, 12 mg qd for 2 consecutive weeks followed by 1-week discontinuation was generally recognized as the recommended regimen for subsequent studies, and 12 mg qd was the maximum tolerated dose. In addition, the study results showed that the  $t_{max}$  of anlotinib in humans was increased with a high-fat diet as compared to administration under fasting conditions, and drug absorption was slightly reduced (approximately 80% that of administration under fasting conditions). Therefore, anlotinib is recommended to be administered under fasting conditions in subsequent clinical practice.

Anlotinib hydrochloride will be administered orally to all enrolled patients at a dose of 12 mg qd before breakfast, for 2 consecutive weeks, and discontinued for 1 week, i.e., three weeks (21 days) as a course of treatment. Treatment should continue until disease progression or occurrence of intolerable adverse reactions.

### 4.4 Dose Adjustment

Adverse reactions should be closely monitored during the administration of the study drug, and the dose should be adjusted according to the patient's tolerance. Adverse reactions caused by the study drug can be treated by symptomatic treatment, drug interruption and/or dose adjustment. The dose should be adjusted under the guidance of a physician according to the severity of adverse reactions: 1) First dose adjustment: 10 mg qd for 2 weeks, followed by 1-week discontinuation; 2) Second dose adjustment: 8 mg qd for 2 weeks, followed by 1-week discontinuation. If the dose of 8 mg remains intolerable, the drug should be permanently discontinued.

Dose adjustments for each adverse reaction are as follows:

- **Hematologic Toxicities**

(1) Platelet count decreased

Grade of AE	Treatment Recommendations	Dose Adjustment
Grade 1	Perform visits as scheduled	Maintain the original dose

Grade 2	Delay dosing until AE resolves to $\leq$ grade 1	Maintain the original dose
Grade 3	Delay dosing and provide medical interventions until AE resolves to $\leq$ grade 1	Continue at a lower dose
Grade 4	Permanent discontinuation	/

(2) Neutrophil count decreased

Grade of AE	Treatment Recommendations	Dose Adjustment
Grade 1	Perform visits as scheduled	Maintain the original dose
Grade 2	Delay dosing until AE resolves to $\leq$ grade 1	Maintain the original dose
Grade 3-4	Delay dosing and provide medical interventions until AE resolves to $\leq$ grade 1	Continue at a lower dose

● **Non-Hematologic Toxicities**

(1) Hepatic function abnormal (elevated ALT, AST or TBIL)

Grade of AE	Treatment Recommendations	Dose Adjustment
Grade 1	Perform visits as scheduled	Maintain the original dose
Grade 2	Delay dosing until AE resolves to $\leq$ grade 1	Maintain the original dose
Grade 3-4	Delay dosing and provide medical interventions until AE resolves to $\leq$ grade 1	Continue at a lower dose

(2) Proteinuria

Grade of AE	Definition	Treatment Recommendations	Dose Adjustment
Grade 1	1+ proteinuria, or urine protein $<$ 1.0 g/24 h	Perform visits as scheduled	Maintain the original dose
Grade 2	2+ proteinuria, and urine protein $<$ 1.0 g/24 h	Perform visits as scheduled	Maintain the original dose
	2+ proteinuria, and urine protein is 1.0–3.4 g/24 h	Delay dosing and provide medical interventions until proteinuria $\leq$ 2+ and urine protein $<$ 1.0 g/24 h	Maintain the original dose
Grade 3-4	Urine protein $\geq$ 3.5 g/24 h;	Delay dosing and provide medical interventions until proteinuria $\leq$ 2+ and urine protein $<$ 1.0 g/24 h	Continue at a lower dose

(3) Hemorrhage events (including hemoptysis, digestive tract hemorrhage, nasal hemorrhage, bronchial hemorrhage, gingival hemorrhage, gross hematuria, fecal occult blood, and cerebral hemorrhage)

Grade of AE	Treatment Recommendations	Dose Adjustment
Grade 1	Perform visits as scheduled	Maintain the original dose
Grade 2	Delay dosing until AE resolves to $\leq$ grade 1	Continue at a lower dose; if event recurs, consider permanent discontinuation
$\geq$ Grade 3	Permanent discontinuation	/

#### (4) Hypertension

Grade of AE	Treatment Recommendations	Dose Adjustment
Grade 1-2	Perform visits as scheduled	Maintain the original dose
Grade 3	Delay dosing until AE resolves to $\leq$ grade 2	Continue at a lower dose
Grade 4	Permanent discontinuation	/

#### (5) Hand and foot skin reaction

Grade of AE	Treatment Recommendations	Dose Adjustment
Grade 1-2	Perform visits as scheduled	Maintain the original dose
Grade 3-4	Delay dosing until AE resolves to $\leq$ grade 2	Continue at a lower dose

#### (6) Others

Grade of AE	Treatment Recommendations	Dose Adjustment
Grade 1	Perform visits as scheduled	Maintain the original dose
Grade 2-3	Delay dosing until AE resolves to $\leq$ grade 1	Continue at a lower dose
Grade 4	Permanent discontinuation	/

